7.4.1.2.2 Chronicity

Single occasion:	Single event with limited duration
Intermittent:	Several episodes of an event, each of limited duration
Persistent:	Event which remained indefinitely

7.4.1.2.3 Causality

The Investigator will assess causal relationship between the study medication and each adverse event, and answer "yes" or "no" to the question, "Do you consider that there is a reasonable possibility that the event may have been caused by the study medication?"

For SAEs, causal relationship will also be assessed for study procedures, additional study medication, and other medication. Note that for SAEs that could be associated with any study procedure, the causal relationship is implied as "yes".

A guide to the interpretation of the causality question is found in Section [14.2](#).

7.4.1.2.4 *Action and Outcome*

- Action taken with study medication (none, study medication stopped, study medication temporarily interrupted)
- Other actions (none, concomitant medication, study discontinuation, hospitalization, other)
- The outcome and date of outcome according to the following definitions:
 - Recovered or resolved (adverse event disappeared)
 - Recovering or resolving (patient is recovering)
 - Not recovered or not resolved (adverse event remains without signs of improvement)
 - Recovered or resolved with sequelae (adverse event has resulted in permanent disability or incapacity)
 - Fatal
 - Unknown (only applicable if patient has been lost to follow-up)
- Seriousness (yes or no)

7.4.1.3 *Reporting Procedure for SAEs*

The Investigator must report all SAEs to the Sponsor as soon as practical, but in all cases within 24 hours of awareness. Any fatal SAEs notified in the 28-day period after the last dose of study drug must also be reported.

SUSARs will be determined by the Sponsor's Medical Monitor.

SAEs will be reported to the IRB and regulatory authority(ies) according to local requirements.

All adverse events will be followed until they have abated, or until a stable situation has been reached. Depending on the event, follow up may require additional tests or medical procedures as indicated, and/or referral to the patient's general physician or a medical specialist.

It is the responsibility of the Investigator to ensure that any necessary additional therapeutic measures and follow-up procedures are performed.

7.4.2 *Pregnancy*

In addition to the Screening serum pregnancy test (see Section 7.1.4), urine pregnancy tests will also be performed by the study center on women of childbearing potential at Screening (confirmed to be negative prior to the chest X-ray) and during the study.

Should a female patient become pregnant, or if a male patient fathers a child during the study or in the 30 days after the end of the study, the Investigator must be informed immediately. The Investigator will report this information to the Sponsor within 7 days of awareness. The Investigator will make all reasonable efforts to ascertain the progress and outcome of the pregnancy. If the outcome meets the criteria for immediate classification of a SAE (e.g. spontaneous or therapeutic abortion, stillbirth, neonatal death, congenital anomaly, birth defect) the Investigator must follow the procedure for reporting SAEs.

7.4.3 Laboratory Assessments

In addition to the laboratory tests detailed below, unscheduled and/or repeat testing may be performed at the discretion of the Investigator. Any additional laboratory results will also be merged into the final database. Laboratory results will be provided to the Investigator for each patient and each visit. The Investigator should assign whether each abnormal result is not clinically significant or a clinically significant.

Samples will be taken and handled according to the laboratory manual and analyzed locally.

7.4.3.1 *Hematology*

The following will be measured: hemoglobin, hematocrit, total white cell count, leukocyte differential count and platelet count.

For each assessment, a sample of venous blood will be collected in a collection tube containing ethylenediaminetetraacetic acid (EDTA).

7.4.3.2 *Blood Chemistry*

The following will be measured: creatinine, total bilirubin, alkaline phosphatase, aspartate aminotransferase, alanine transaminase, gamma-glutamyl transferase, lactate dehydrogenase, creatine kinase, thyroid stimulating hormone, triiodothyronine and thyroxine, glucose, potassium, sodium and calcium.

For each assessment, a sample of venous blood will be collected in a vacutainer collection tube.

7.4.3.3 *Urinalysis*

A midstream urine sample will be collected in a sterile container. The following will be tested: leukocytes, blood, ketones, bilirubin, urobilinogen, protein and glucose. If urinalysis on dipstick is positive for leukocytes and/or blood/hemoglobin, a microscopic examination including erythrocytes, leukocytes, bacteria, casts, epithelial cells and crystals will be performed.

7.4.4 Vital Signs

The vital signs to be collected are blood pressure and pulse rate.

Post-dose measurements will be taken in relation to the morning dose. Therefore, 12-hour measurements will be taken prior to the evening dose.

For each assessment, supine vital signs will be assessed while the patient has been at rest for at least 5 minutes.

7.4.5 Physical Examination

A full physical examination, covering major body systems (assessments of the nose, throat, skin, thyroid gland, neurological system, respiratory system, cardiovascular system, abdomen [liver and spleen], lymph nodes and extremities) will be performed at Screening. Results will be recorded in the eCRF as normal, abnormal not clinically significant or abnormal clinically significant and abnormal results described. The full physical examination will be repeated at the End of Study Visit, and any changes only recorded.

A brief physical examination, including assessments of the skin, respiratory system, cardiovascular system, and abdomen (liver and spleen) will be performed pre-dose for Part A, and pre-dose on Days 1 and 7 for Part B.

7.4.6 12-Lead ECG

Each 12-lead ECG should be taken after at least 5 minutes in the supine position. An overall assessment (normal, abnormal not clinically significant or abnormal clinically significant) will be recorded in the eCRF by the Investigator. ECG recordings will be assessed locally.

Post-dose measurements in Part A will be taken in relation to the single, morning dose of RPL554 or placebo.

8 QUALITY ASSURANCE AND QUALITY CONTROL

The study will be conducted in accordance with the current approved protocol, standard operating procedures and all applicable guidelines and requirements (see Section 10).

8.1 Audit and Inspection

The Sponsor, or its designee may conduct a quality assurance audit. An inspection of this study may also be carried out by regulatory authorities at their discretion. Such audits or inspections can occur at any time during or after completion of the study. If an audit or inspection occurs, the Investigator and institution agree to allow the auditor/inspector direct access to all relevant documents and to allocate his time and the time of his staff to the auditor or inspector to discuss findings and any relevant issues.

8.2 Monitoring and Source Document Verification

The study will be monitored by a monitor approved by the Sponsor. During these visits, all procedures will be monitored for compliance with the protocol. Source documents will be reviewed and compared with the data entries in the eCRFs to ensure consistency. The Sponsor will ensure that the study is monitored in accordance with the principles of ICH GCP. The frequency of monitoring visits will be determined, in part, by the rate of patient recruitment.

The following are examples of items that will be reviewed at these visits:

- Compliance with the protocol
- Consent procedure
- Source documents
- Adverse event procedures
- Storage and accountability of materials

The monitoring visits also provide the Sponsor with the opportunity to ensure that timely patient accrual and the other Investigator's obligations and all applicable requirements are being fulfilled.

The Investigator must permit the study monitor, the IRB, the Sponsor's auditors and representatives from regulatory authorities direct access to all source documents for confirmation of the accuracy and reliability of data contained within the eCRFs (source document verification). Patient confidentiality will be protected at all times.

Source documents are defined as the results of original observations and activities of a clinical investigation, including medical notes. All source documents produced in this study will be maintained by the Investigator and made available for inspection. The original signed informed consent form for each patient will be retained by the Investigator and the second signed original given to the patient.

Source data include, but is not limited to, the following and will be identified in a source data location log:

- Screening/enrolment log
- Medical notes - which should be updated after each visit to include visit dates, medical history, diagnosis of COPD, concomitant medication, any clinically relevant findings of clinical examinations or clinically relevant adverse events/medication changes, SAEs and information on patient withdrawal
- Informed consent form
- 12-lead ECGs
- Laboratory reports
- Visit dates
- Study medication accountability/inventory forms

The study monitor will carry out source document verification at regular intervals. This is an essential element of quality control, as it allows the rectification of transcription errors and omissions.

8.3 Data Management and Coding

Data for each patient will be recorded in an eCRF. Data collection must be completed for each patient who signs an informed consent form and receives at least one dose of study medication.

eCRFs will be designed and produced by the Sponsor or designee and should be completed in accordance with instructions. The Investigator is responsible for maintaining adequate and accurate medical records from which accurate information will be transcribed directly into the eCRFs using a secure internet connection. The eCRFs should be filled out completely by the Investigator or designee as stated on the delegation of responsibilities form. The eCRF system will be Food and Drug Administration Code of Federal Regulations 21 Part 11 compliant.

The eCRFs must be reviewed, signed and dated by the Investigator.

Data entered into the eCRF will be validated as defined in the data validation plan. Validation includes, but is not limited to, validity checks (e.g. range checks), consistency checks and customized checks (logical checks between variables to ensure that study data are accurately reported) for eCRF data and external data. A majority of edit checks will be triggered during data entry and will therefore facilitate efficient 'point of entry' data cleaning.

Data management personnel will perform both manual eCRF review and review of additional electronic edit checks to ensure that the data are complete, consistent and reasonable. The electronic edit checks will run continually throughout the course of the study and the issues will be reviewed manually online to determine what action needs to be taken.

Manual queries may be added to the system by clinical data management or study monitor. Clinical data managers and study monitors are able to remotely and proactively monitor the patient eCRFs to improve data quality.

External data (laboratory safety, 12-lead ECG and PK data) will be transferred electronically into the study database. Discrepancies will be queried to the site and/or the laboratory until the electronic data and the database are reconciled.

All updates to queried data will be made by authorized study center personnel only and all modifications to the database will be recorded in an audit trail. Once all the queries have been resolved, eCRFs will be locked by password protection. Any changes to locked eCRFs will be approved by the Investigator.

Once the full set of eCRFs have been completed and locked, the Sponsor will authorize database lock and all electronic data will be sent to the designated statistician for analysis. Subsequent changes to the database will then only be made only by written agreement of the Sponsor.

Adverse events will be coded from the verbatim description (Investigator term) using the Medical Dictionary for Regulatory Activities (MedDRA). Prior and concomitant medications will be coded according to the World Health Organization drug code. An independent coding review will be performed by the Sponsor.

The clinical database (in Statistical Analysis System [SAS] format) will be transferred to the Sponsor at the end of the study.

9 STATISTICAL METHODS

9.1 Statistical and Analytical Plans

This section presents a summary of the planned statistical analyses. A detailed plan describing the analyses to be conducted will be defined before the last patient is completed and will include the determination of rules for major and minor protocol deviations. Any deviation from the analysis specified in the protocol or the statistical analysis plan will be detailed and justified in the clinical study report.

9.2 Populations to be Analyzed

Allocation of patients to the analysis populations (and whether any patients or specific data from a patient will be excluded) will be determined at the pre-database lock meeting.

Part A:

The full analysis set will consist of all randomized patients with sufficient data collected after intake of study treatment to compute the efficacy/pharmacodynamic parameters.

The safety set will consist of all randomized and treated patients.

The PK data set will consist of all randomized patients with blood sampling performed after an RPL544 treatment and with data sufficient to calculate PK parameters.

Part B:

The full analysis set will consist of all randomized patients with sufficient data collected after intake of study treatment to compute the efficacy/pharmacodynamic parameters on at least two treatment periods.

The completer analysis set will consist of all randomized patients that complete all treatment periods.

The safety set will consist of all randomized patients who took at least one dose of study treatment during at least one period.

The PK data set will consist of all randomized patients with blood sampling performed after at least one dose of RPL544 and with data sufficient to calculate PK parameters.

9.3 Study Endpoints

9.3.1 Part A

9.3.1.1 *Primary Endpoint*

The primary endpoints in Part A are the pharmacokinetic parameters AUC_{0-12} and AUC_{0-t} , maximum concentration (C_{max}), time to maximum concentration (t_{max}) and half-life.

9.3.1.2 Secondary Endpoints

- Safety and tolerability:
 - Continuous monitoring of adverse events
 - Laboratory safety tests [hematology, blood chemistry and urinalysis]
 - 12-lead ECG (including QTcF and heart rate), supine vital signs (blood pressure and pulse rate)
- Change from baseline in average FEV₁ AUC_{0-4h} measured after single dose
- Change from baseline in average FEV₁ AUC_{0-12h} measured after single dose
- Change from baseline in peak FEV₁ measured after single dose
- Change from baseline in peak pulse and peak heart rate measured after single dose

9.3.2 Part B

9.3.2.1 Primary Endpoint

The primary endpoint in Part B is change from baseline in peak FEV₁ measured after morning dosing on Day 7.

9.3.2.2 Secondary Endpoints

- Safety and tolerability:
 - Continuous monitoring of adverse events
 - Laboratory safety tests (hematology, blood chemistry and urinalysis)
 - 12-lead ECG (including QTcF and heart rate), supine vital signs (blood pressure and pulse rate)
- Change from baseline in (morning) trough FEV₁ measured prior to morning dosing on Day 7
- Change from baseline in peak FEV₁ measured after first dose
- Change from baseline in average FEV₁ AUC_{0-4h} measured after morning dosing on Day 7
- Change from baseline in average FEV₁ AUC_{0-12h} measured after first dose and after morning dosing on Day 7
- Determination of onset of action (>10% increase in FEV₁ from pre- to post- first dose, censored at 120 minutes) after first dose
- RPL554 steady state pharmacokinetics (AUC_{0-12h}, C_{max}, t_{max}, accumulation ratio) after dose 13 on Day 7
- Change from baseline in peak pulse after first dose on Day 1 and after morning dosing on Day 7
- Change from baseline in average FEV₁ AUC_{0-4h} and average FEV₁ AUC_{0-12h} on Day 1
- Change from baseline in rescue medication use

9.3.2.3 *Exploratory Endpoint*

- Evaluation of dose response of RPL554 on peak and average FEV₁ AUC_{0-12h} after morning dose on Day 7, and morning trough FEV₁ prior to the last dose on Day 7
- Change from baseline in Likert dyspnea scale measured after single dose and after morning dose on Day 7

9.4 *Statistical Methods*

In general, unless stated otherwise, continuous variables will be summarized using descriptive statistics (number of patients, mean, standard deviation, median, minimum and maximum values) and for categorical (nominal) variables, the number and percentage of patients will be used.

All hypothesis testing will be done using two-sided alternative hypotheses. P-values less than 5% will be considered statistically significant.

9.4.1 *Patient Disposition*

The number of patients enrolled, randomized, completed or withdrawn (with reason for withdrawal) will be summarized.

9.4.2 *Protocol Deviations*

All protocol deviations collected will be divided into critical, major or minor categories. Prior to database lock protocol deviations will be reviewed and consequences for inclusion of patients in various analysis population sets determined and documented.

9.4.3 *Demographics and Other Baseline Characteristics*

Demographics and baseline characteristics (including pre- and post-bronchodilator FEV₁ [both in liters and in percentage of predicted normal], post-bronchodilator FEV₁/FVC, FEV₁ reversibility, duration of COPD [time since diagnosis], smoking habits including number of pack years, number of patients taking COPD medications by therapeutic class including ICS, LABA, LAMA or combinations thereof) will be listed and summarized appropriately.

Medical history, prior and concomitant medications, viral serology results, pregnancy test results from females and chest X-ray findings will be listed.

9.4.4 *Extent of Exposure and Treatment Compliance*

For Part A, all administration of study treatment will be performed at the clinic under supervision of the study staff; therefore, no formal analysis of compliance will be performed.

For Part B, compliance will be calculated based on the number of capsules dispensed and returned. Total exposure will be based on the compliance with dose and the dose group the subject was randomized into.

9.4.5 Efficacy/Pharmacodynamics

FEV₁ and FVC will be summarized as actual value and change from baseline using descriptive statistics over time for all treatments and both study parts.

The peak effect on FEV₁ during these time intervals will be computed as the maximum value in the 4 hours after dosing. The average effect (average FEV₁ AUC_{0-t}) will be calculated as the AUC divided by the length of the time interval of interest. For analysis of the peak, average and trough FEV₁, the change from baseline will be expressed as the parameter divided by the pre-dose Day 1 baseline value.

In Part A, computed pharmacodynamic parameters for FEV₁ will be compared between the treatments using analysis of covariance models with fixed factor treatment, and using the pre-dose baseline value as a covariate. In Part B, computed pharmacodynamic parameters (peak, AUC₀₋₄, AUC₀₋₁₂ and trough) for FEV₁ will be compared between the treatments using analysis of covariance models adjusting for treatment period and patient, and using the pre-dose Day 1 baseline value as a covariate. FEV₁ will be analyzed using multiplicative models, which means that data (dependent and baseline) are logged prior to analysis and the result then transformed back to the linear scale giving treatment differences as ratios of geometric means.

Primarily, active treatments will be compared to placebo. For RPL554 DPI, the high dose will first be compared to placebo, and if found statistically significant then the next lower dose will be compared to placebo, and if found statistically significant then the subsequent lower dose will be compared to placebo, and this procedure repeated for all doses. Secondarily, the different doses of RPL554 DPI will be compared. Results of the comparisons will be expressed as the mean geometric ratio with 95% confidence intervals and associated, 2-sided, p-value.

Onset of action will be calculated and summarized by treatment. In Part B, a Kaplan-Meier plot illustrating time to onset will be constructed and from the survival curves the median time to onset will be estimated. Placebo will not be included in summaries of onset of action.

In Part B, the average use of rescue medication during the treatment periods will be summarized by treatment group. In addition, all rescue medication used during the treatment visits (Day 1 in Part A and Days 1 and 7 in Part B) will be listed to assess the accuracy of the FEV₁ recordings.

In Part B, change in Likert dyspnea scale to each time point will be compared between the treatments using analysis of covariance models adjusting for factors for treatment, period and patient, and using the pre-dose Day 1 baseline value as a covariate. Additive models will be used for dyspnea.

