2.2.2 Secondary Objectives

- To investigate the safety and tolerability of repeat doses of RPL554, administered by DPI
- To investigate the bronchodilator effect of RPL554 administered by DPI, in terms of average FEV₁ AUC_{0-4h}, average FEV₁ AUC_{0-12h} and trough FEV₁
- To determine the onset of action of RPL554 administered by DPI
- To evaluate the PK profile of RPL554 administered by DPI
- To evaluate the amount of rescue medication use during treatment periods

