6.2 Screening

Written informed consent will be obtained by the Investigator as specified in Section 10.3 prior to any study related procedures being performed. This typically will need to be performed prior to the Screening visit to allow for discontinuation of any prohibited medications (see Section 5.8.1). Screening procedures may be performed over more than 1 day.

Patients will be screened to determine eligibility against the Inclusion and Exclusion Criteria between 7 and 14 days before the first dose of study treatment. Patients must observe the medication restrictions described in Section 5.8.1, and other restrictions described in Section 6.1. To account for diurnal variability in pulmonary function, the Screening visit is to take place in the morning.

The following assessments will be performed, generally in the order indicated (to the extent feasible):

- Obtain informed consent (if not done prior to Screening)
- Recording of demographic information, including height and weight
- Recording of medical/surgical and disease history
- Recording of prior medications and therapies; confirming that medications were withheld as required
- Vital signs
- Full physical examination (see Section 7.4.5)
- 12-lead ECG
- Reversibility test:
 - Pre-reversibility spirometry
 - Four puffs of albuterol
 - Post-reversibility spirometry (20 to 30 minutes after albuterol)

- Blood samples for laboratory screening and safety tests:
 - Viral serology
 - Follicle stimulating hormone (FSH; if required to confirm post-menopausal status)
 - Serum pregnancy (for women of childbearing potential only)
 - Hematology and blood chemistry
- Urinalysis
- Urine pregnancy (for women of childbearing potential only) – results should be obtained prior to the chest X-ray
- Chest X-ray (unless historical X-ray performed in last 12 months is available)
- Questioning for adverse events

If the patient meets all of the Inclusion and none of the Exclusion Criteria:

- Instruct patient to return in 7 to 14 days for Part A treatment

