AUC_{0-12h} FEV₁ is defined and derived similarly to AUC_{0-4h} above, but over 12-hours post-dose. If patient misses hours 11 and 12 then the AUC_{0-12h} is set to missing.

Morning trough FEV₁ is the average of the FEV₁ pre-dose assessments (-60 minutes and -5 minutes) on Day 7 and the change from baseline will be analyzed similarly to AUC_{0-4h} and AUC_{0-12h}.

15.2.1.2. Change in baseline in peak FEV₁ measured after first dose, average FEV₁ of AUC_{0-4h} on Day 1 and average FEV₁ of AUC_{0-12h} FEV₁ on Day 1 (Secondary variables 4, 5 and 6)

Peak FEV₁ measured after first dose is defined as the peak FEV₁ (after 4 hours of dosing) on Day 1. It is defined as the change from baseline to peak FEV₁ and derived similarly to primary analysis (see [section 15.1.1](#)), but instead at Day 1.

AUC_{0-4h} FEV₁ and AUC_{0-12h} FEV₁ on Day 1 are defined and derived similarly to secondary endpoint above (see [section 15.2.1.1](#)), but at Day 1. Parameters will be calculated over 4 and 12 hours, respectively (on Day 1 of each treatment period). If patient misses hours 2 and 4 then the AUC_{0-4h} is set to missing. Similarly, if patient misses hours 11 and 12 then the AUC_{0-12h} is set to missing. If the assessment at 12-hours is missing, the AUC result will be divided by the actual time of the last collected assessment.

15.2.1.3. Determination of onset of action (>10% increase in FEV₁, from pre-first dose, censored at 120 minutes) on Day 1 (Secondary variable 7)

Onset of action is defined as a >10% increase in FEV₁ from pre-dose on Day 1 over the next 120 minutes (2 hours) after morning dosing on Day 1 (5, 15 and 30 minutes and 1, 1.5, 2 hours). Time to onset will be derived as the time to onset of action is achieved. For analysis purposes, it will be assumed that the pre-dose value occurred at time 0. Patients not experiencing an onset of action will be censored at 120 minutes (2 hours) or at time of premature discontinuation (if withdrawn before 120 minutes). If the number of patient censored regarding onset of action is deemed to be too high (number of patients with onset of action censored >50%), the Kaplan-Meier estimates and

Document: Z:\RPL554\AZA40375\Biostatistics\Documentation\SAP\Verona RPL554-DP-201 SAP v2.0 – Part B

Author: [name] / [name]

Version Number: 2.0

Version Date: [08JUL2019]

Template No.: CS_TP_BS016 Revision 5

Reference: CS_WI_BS005

Effective Date: 01Apr2018

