Copyright © 2009, 2010, 2012, 2016, 2018 IQVIA. All rights reserved. The contents of this document are confidential and proprietary to IQVIA Holdings Inc. and its subsidiaries. Unauthorized use, disclosure or reproduction is strictly prohibited.

accompanying figure will not be presented. Patients receiving placebo will not be summarized in either tables or figure.

15.2.1.4. RPL554 steady state pharmacokinetics (AUC_{0-12h}, Cmax, time to maximum concentration [tmax]) (Secondary variable 8)

Concentration of RPL554 and computed PK parameters (AUC_{0-12h}, C_{max} [maximum concentration], t_{max} [time to maximum concentration]) on Day 7 of each treatment period (pre-dose, 30 minutes and 1, 1.5, 2, 4, 8 and 12-hours post dose).

15.2.1.5. Change from baseline in rescue medication use during treatment periods (Secondary variable 9)

The average use, in terms of weight (mcg) of rescue medication during the treatment periods will be collected from the Rescue Medication Canister Dispensed and Rescue Medication Canister Weight eCRF pages and will be summarized by treatment group. Rescue medication used will be calculated from the difference in weight at time of dispensing and weight at time of collection. So, change from baseline is the difference in rescue medication from baseline (at pre-dose on Day 1) and the collection visit (12hr post-dose on Day 7).

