Summary statistics for each parameter will be presented for baseline, at point of interest (if applicable) and change from baseline by treatment group on patients with both assessments, on the original scale.

Document: Z:\RPL554\AZA40375\Biostatistics\Documentation\SAP\Verona RPL554-DP-201 SAP v2.0 – Part B

Author: [name] / [name]

Version Number: 2.0

Version Date: [08JUL2019]

Template No.: CS_TP_BS016 Revision 5

Reference: CS_WI_BS005

Effective Date: 01Apr2018

Copyright © 2009, 2010, 2012, 2016, 2018 IQVIA. All rights reserved. The contents of this document are confidential and proprietary to IQVIA Holdings Inc. and its subsidiaries. Unauthorized use, disclosure or reproduction is strictly prohibited.

15.2.3.2. Analysis of Secondary Variable 7

Onset of action will be summarized by treatment and a Kaplan-Meier plot illustrating time to onset constructed. The SAS® procedure LIFETEST, will be used as follows to calculate the median, 25th and 75th percentile:

```
PROC LIFETEST DATA=... OUTSURV =... CONFTYPE = LINEAR METHOD =  
KM ALPHA = 0.05 ALPHAQT = 0.05 PLOTS = (SURVIVAL (FAILURE NOCENSOR));  
    TIME ONSET*STATUS (1);  
    STRATA TREATMENT;  
RUN;
```

where ONSET = time to onset of action

TREATMENT = treatment group (Respective dose of RPL554, 150 μ g, 500 μ g, 1500 μ g and 3000 μ g)

STATUS (1) = indicates an event of onset of action

To calculate the mean difference to RPL554 3000 μ g, the SAS procedure LIFETEST will be carried for each treatment comparison pair individually.

If a patient does not have onset of action from pre-dose on Day 1 over the next 120 minutes (2 hours) the data will be censored at 120 minutes or if a patient prematurely discontinued before 120 minutes, the last available assessment time post-dose (1 indicates censored variables). Median differences to the highest dose (RPL554 3000 μ g) will be estimated and the p-value based on the PROC LIFETEST above (Wilcoxon signed rank sum test) between each treatment groups and the highest dose will also be presented.

15.2.3.3. Analysis of Secondary Variable 8

As described in [section 4.3](#), this SAP will not summarise the analyses related to the PK concentrations and parameters and this will be handled by a third-party vendor.

15.2.3.4. Analysis of Secondary Variable 9

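### Placebo is left out of the onset-of-action summaries, so the responder and time-to-onset results have no background rate to be read against

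*Protocol*

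**What the plan says.** The objective (Protocol 2.2.2) is "To determine the onset of action of RPL554 administered by DPI". The endpoint (Protocol 9.3.2.2) is "Determination of onset of action (>10% increase in FEV₁ from pre- to post- first dose, censored at 120 minutes) after first dose". SAP Part B 15.2.1.3 fixes the assessment times as "after morning dosing on Day 1 (5, 15 and 30 minutes and 1, 1.5, 2 hours", which makes six readings. Neither document requires a second reading to confirm the rise.

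Both documents exclude placebo. Protocol 9.4.5: "Placebo will not be included in summaries of onset of action". SAP Part B 15.2.1.3: "Patients receiving placebo will not be summarized in either tables or figure". Neither gives a reason.

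SAP Part B 15.2.3.2 plans Kaplan-Meier estimates by dose (median and quartiles), and a p-value "between each treatment groups and the highest dose will also be presented". No onset comparison with placebo is planned. SAP Part B 15.2.1.3 also withholds the Kaplan-Meier estimates and figure when censoring is too heavy, defined as "number of patients with onset of action censored >50" percent.

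**The concern.** A fixed threshold tested six times without confirmation will sometimes be crossed when nothing has changed except the reading. The share of crossings that would have happened anyway is what a placebo period measures, and each patient is planned to have one with the same Day 1 spirometry (Protocol 5.1.2 and 6.4.1.3). The plan collects those readings and then does not derive onset from them.

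The contrast with 3000 µg cannot stand in for placebo. Chance crossings occur at every dose, so comparing two doses does not show what part of either result is due to drug. At stake is the reading of a secondary endpoint: the proportion of patients with onset and the time to onset at each dose, most of all at weaker doses whose true effect lies near or below the 10% threshold.

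**Working it through.** **The plan's own variability figure.** Protocol 9.5 assumes a residual CV of 6% for peak FEV₁ and states that 30 patients give 80% power for a 4.6% difference. On the log scale SD = √ln(1 + 0.06²) = 0.0599 and SE = 0.0599 × √(2/30) = 0.0155. The noncentral t with 29 df gives a detectable log difference of 0.0449, that is 4.59%, and 0.046 × 1.5 L = 0.069 L. The figure reproduces. It also shows what the 6% is: residual variability between treatment periods in the crossover, not reading-to-reading variability within a session. It is used below only as the upper end of an assumed range.

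**Inputs.** From the documents: threshold ln(1.10) = 0.0953; six post-dose readings; two pre-dose readings on Day 1 (Protocol 6.4.1.1). SAP Part B 15.2.1.3 does not say whether onset is judged against their mean or a single one, so both are shown. Assumed: within-session CV of 3% to 6%; either none or half of that variance shared by all readings of a visit, so that the shared part cancels; normal log errors; no drug effect; no drift.

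**One reading.** At CV 6% with independent readings, the chance that a given reading crosses is 1 − Φ(0.0953 / (0.0599 × √2)) = 1 − Φ(1.124), about 13%, against a single pre-dose reading. Against the mean of two it is 1 − Φ(0.0953 / (0.0599 × √1.5)) = 1 − Φ(1.298), about 10%.

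**Any of six readings.** Let s be the SD of the unshared part, s = √ln(1 + CV²) × √(1 − shared fraction), and let b be the baseline error, with SD s for one reading or s/√2 for the mean of two. The chance rate is the average over b of 1 − Φ((0.0953 + b)/s)⁶. Simulation with 400,000 placebo periods per setting gives the figures below, and numerical integration agrees within 0.1 percentage point.

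| CV | Independent, mean of two | Independent, single | Half shared, mean of two | Half shared, single |
|---|---|---|---|---|
| 3% | 2.5% | 5.6% | 0.1% | 0.4% |
| 4% | 12.3% | 17.3% | 1.6% | 4.0% |
| 5% | 24.9% | 29.3% | 7.0% | 11.5% |
| 6% | 36.2% | 39.0% | 15.3% | 20.4% |

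**The 50% censoring rule.** The SAP does not say whether it applies per dose or pooled. Assume per dose with n = 30: the output is shown when at least 15 patients have onset. For a dose with no effect, the binomial probability of 15 or more onsets is below 0.01% at a 17% chance rate, 0.3% at 25%, 1.2% at 29%, 8% at 36% and 15% at 39%.

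**A weak dose.** As an illustration, take a constant true rise of 4.6% from the first reading. It is below the 10% threshold, so without reading variability nobody would cross. Replacing 0.0953 by 0.0953 − ln(1.046) = 0.0503 in the formula, at CV 6% and with the mean of two pre-dose readings, gives about 67% with onset if readings are independent (36% with no effect) and about 53% if half the variance is shared (15% with no effect). Such a dose would have 15 or more onsets out of 30 with probability about 98% and 68% respectively.

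**The case against.** The exclusion is deliberate and the two documents agree. Onset is a secondary, largely descriptive endpoint, and no confirmatory conclusion rests on it. That stands, and it limits the weight of the point.

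A reader might infer that early response has no placebo control at all. The documents do not support that. FEV₁ is summarised by timepoint for all treatments (Protocol 9.4.5, SAP Part B 15.1.1), a figure shows mean change over time by treatment and day (15.1.3), and Day 1 peak and AUC₀₋₄ₕ are tested against placebo (15.2.1.2 and 15.2.3.1). What is missing is narrower: the patient-level crossing rate and time to crossing on placebo, which mean curves do not yield.

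A reader might also infer that the published medians would be noise. The censoring rule would usually withhold a median driven by chance alone, as the binomial figures show. It does not deal with a weak effect topped up by chance crossings, because those crossings reduce censoring and help the dose pass.

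A third inference is that morning drift must inflate onset. Protocol 6.2 says "To account for diurnal variability in pulmonary function, the Screening visit is to take place in the morning", but that concerns when Screening is scheduled. It does not establish that FEV₁ rises in the two hours after dosing, so no drift is counted here.

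Finally, the comparison with 3000 µg is not shown to be inflated. Background shared by both doses tends to dilute a difference rather than create one. That is correct. The limitation is that this comparison does not answer the placebo question.

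**Conclusion.** The point holds for the responder and time-to-onset analysis only. As planned, drug onset cannot be separated from background crossings there, although the placebo readings needed to do so are collected in the same patients. With an assumed within-session CV of 3% to 6%, the background rate by 120 minutes lies between about 0.1% and about 39%. The width of that range reflects two things the documents do not give: the within-session CV and the share of variance common to a visit. The upper end borrows a between-period CV for peak FEV₁ and should not be read as an estimate. The existence of the gap is certain and its size is not, which is a reason to report the placebo rate rather than assume it. The primary endpoint and the other Day 1 comparisons with placebo are unaffected. The change is worth making, but the trial's main conclusion does not depend on it.

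**What to change.** 1. Delete the placebo exclusion in Protocol 9.4.5 and in SAP Part B 15.2.1.3.
2. Derive onset in the placebo period exactly as in the active periods, and state which pre-dose value is the reference.
3. Add placebo to the onset table: number and percent with onset by 120 minutes, and quartiles where estimable. Add it as a reference curve whenever the Kaplan-Meier figure is presented.
4. Keep the dose-versus-placebo contrast descriptive, or compare the proportion with onset by 120 minutes by a within-patient method such as McNemar's test. Do not use the LIFETEST strata of 15.2.3.2 for it, because they treat periods from the same patients as independent groups.

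The planned comparison with 3000 µg can stay. The cost is a small wording change in both the Protocol and the SAP and one more stratum in an existing program, with no new visits or data. The downside for the sponsor is that low-dose onset results may look less favourable beside the placebo rate.
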